11.5 Appendix 5: Derived and Transformed Data

11.5.1 General

Multiple Measurements at One Time Point

 Generally, mean of the measurements will be calculated, unless replicate FEV₁ or PEF measurements exist in which case the maximum will be utilised, and used in any derivation of summary statistics but if listed, all data will be presented. If there are two values within a time window the value closest to the target day for that window will be used. If values are the same distance from the target then the mean will be taken. Subjects having both High and Low values for Normal Ranges at any post-baseline visits for safety parameters will be counted in both the High and Low categories of 'Any visit post-baseline' row of related summary tables. This will also be applicable to relevant Potential Clinical Importance summary tables.
Study Day

 Calculated as the number of days from randomisation date : 
 Ref Date = Missing → Study Day = Missing Ref Date < Randomisation Date → Study Day = Ref Date – Randomisation Date Ref Date ≥ Randomisation Date → Study Day = Ref Date – (Randomisation Date) + 1

11.5.2 Study Population

Demographics
Age

 GSK standard IDSL algorithms will be used for calculating age where birth date will be imputed as follows: 
 Date and month will be imputed as '30th June' for every subject. Birth date will be presented in listings as 'YYYY'.
Body Mass Index (BMI)

 Calculated as Weight (kg)/Height (m)²
Predicted FEV ₁

 Calculated using (Quanjer, 2012), the website www.ers-education.org/guidelines/global-lung-function-initiative has resources such as a SAS macro and an Individual Subject Excel Spreadsheet downloadable from the Tools section of the website that will be provided to the sites (see SRM).

Extent of Exposure

 Number of days of exposure to study drug will be calculated based on the formula: Duration of Exposure in Days = Number of Weekly Doses

 Subjects who were randomised but did not report a treatment start date and stop date will be categorised as having zero days of exposure.

 The cumulative dose will be based on the formula: Cumulative Dose = Sum of Total Weekly Doses

11.5.3 Safety

ECG Parameters
RR Interval

 IF RR interval (msec) is not provided directly, then RR can be derived as : 
 [1] If QTcB is machine read & QTcF is not provided, then : $RR = \left[\left(\frac{QT}{QTcB} \right)^2 \right] * 1000$ 
 [2] If QTcF is machine read and QTcB is not provided, then: $RR = \left[\left(\frac{QT}{QTcF} \right)^3 \right] * 1000$ If ECGs are manually read, the RR value preceding the measurement QT interval should be a collected value THEN do not derive.
Corrected QT Intervals

 When not entered directly in the eCRF, corrected QT intervals by Bazett's (QTcB) and Fridericia's (QTcF) formulas will be calculated, in msec, depending on the availability of other measurements. IF RR interval (msec) is provided then missing QTcB and/or QTcF will be derived as : $QTcB = \frac{QT}{\sqrt{\frac{RR}{1000}}}$ $QTcF = \frac{QT}{\sqrt[3]{\frac{RR}{1000}}}$

Adverse Events

 MedDRA version 19.0 or later will be used for coding of AE's.
Disease Related Events

 The following DREs are common in subjects with mild allergic asthma and can be serious/life threatening: 
 wheeziness chest tightness or chest heaviness coughing 
The start and stop date/time would be recorded for each DRE. The time since 1st dose and time since most recent dose should be computed for each DRE.

Cytokine Release Syndrome (CRS)

 CRS events will be captured on a modified version of GSK's standard non-serious AE eCRF page. The modification captures whether the item is a CRS event and, if it is, its CRS grading score. For the purposes of summarising data the GSK AE preferred terms (as coded by the dictionary groups using the latest version of MEDDRA) will be mapped to the CRS categories as shown below:

CRS Category	Examples of GSK AE (Verbatim) Terms that might be mapped to each CRS category via MEDDRA	MEDDRA Preferred terms (Codes) Note: Should be cross checked at time of analysis since codes may be superseded if MEDDRA version changes
Headache	Headache	Headache (10019211) Sinus headache (10040744)
Fever	High temperature, feeling hot and cold & shivering	Pyrexia (10037660) Body temperature increased (10005911) Feeling hot (10016334) Hyperhidrosis (10020642)
Chills/Rigors	Shivering & trembling	Chills (10008531) Feeling cold (10016326)
Nausea	Feeling sick	Nausea (10028813)
Vomiting	Being sick	Vomiting (10047700)
Diarrhoea	Loose stools & frequent bowel movements	Diarrhoea (10012735)
Arthralgia	Arthralgia	Arthralgia (10003239) Musculoskeletal stiffness (10052904)
Myalgia	Achy Muscles	Myalgia (10028411) Back pain (10003988) Neck pain (10028836) Pain (10033371) Pain in extremity (10033425)
Hypotension	Low blood pressure	Hypotension (10021097)

Note: The above may not be an exhaustive list. Therefore, prior to unblinding the medical monitor shall review a list of distinct AE preferred terms observed in the study and ensure that they are all assigned/mapped to a single CRS category (if the preferred term does not relate to a CRS category then it can be mapped as non-CRS; further queries may be raised with the sites if a term was not marked by the site as a CRS event but maps to a CRS category via its MEDDRA coding).

- In the event that multiple terms with different CRS grading scores are mapped to the same CRS category the worst case score (highest severity) should be used in any TLFs.
- For each CRS category the total number of occasions (visits) each subject experienced any non-zero grade of CRS event should be derived (should range between 0 and 8 if the subject completed all dosing visits as planned). This should also be expressed as a proportion of the actual dosing visits attended by the subject.
- For each subject and dosing visit combination the number of different CRS event categories should be derived (where the subjects reported any non-zero grade event); e.g. Subject P experienced 3 different CRS event types at dosing visit 1, 0 CRS event types at dosing visit 2, 4 CRS event types at dosing visit 3, etc.

Rescue Medication

[figure not shown]
Rescue medication (e.g. Salbutamol) administered as part of the BAC procedures will not be reported separately (it may be reported as part of the con med listings).

Prior to DBF the medical monitor should review the unique medications in the con med dataset to flag any items that should be classified as rescue medications.

Laboratory Parameters

- If a laboratory value which is expected to have a numeric value for summary purposes, has a non-detectable level reported in the database, where the numeric value is missing, but typically a character value starting with '<x' or '>x' (or indicated as less than x or greater than x in the comment field) is present, the number of significant digits in the observed values will be used to determine how much to add or subtract in order to impute the corresponding numeric value.
 - Example 1: 2 Significant Digits = '< x' becomes x - 0.01
 - Example 2: 1 Significant Digit = '> x' becomes x + 0.1
 - Example 3: 0 Significant Digits = '< x' becomes x - 1

11.5.4 Efficacy

LAR and EAR	
Schematic	
 
FEV₁ Change from Saline (L)
 
Time (H)
 
Legend: Reference (squares), Test (circles)
 
Annotations: EAR, LAR, Min Test LAR, Min Reference LAR, % Attenuation of Test
	
Weighted Mean is defined using the area under the curve divided by the duration of the interval (details below).	
$\text{Percentage Attenuation of Reference Response} = \left(1 - \frac{\text{Test Adjusted Mean}}{\text{Reference Adjusted Mean}} \right) \times 100$	
LAR	
General Considerations	

 FEV₁ measurements taken following the administration of saline will be used as the time zero assessment. In the event that the administration of saline was repeated for safety reasons (saline values must be within 10% of the pre-saline values) the latest saline FEV₁ values prior to the administration of allergen will be used. Pre-saline FEV₁ values and the FEV₁ values recorded as part of the allergen concentration selection phase in the Incremental BAC challenge (Screening visit 2) are not expected to be used in the statistical analysis of the BAC data but will be included in the subject listings if available (e.g. should the coasting procedure occur then it is only planned to database the FEV₁ values associated with the final outcome but any repeat pre-saline values may be captured). 	
Weighted Mean LAR	

 Weighted mean will be calculated for FEV₁ using the linear trapezoidal rule (see formula below). Actual relative times will be used for the calculation except where actual times are missing. If any actual times are missing, planned relative time will be used for these 	

LAR and EAR

observations. Actual relative time will be the time relative to the last inhalation stop time.

- The weighted mean will be calculated as the $AUC_{(t_f - t_l)}$ divided by the $t_f - t_l$ hrs time interval for each subject (t_f = time of first observation, t_l = time for last observation).

$$\text{Weighted Mean } (f - l) = \frac{1}{2} \sum_{f-l} \frac{(C_{i+1} + C_i)(t_{i+1} - t_i)}{t_f - t_l}$$

where,

C_i = highest FEV_1 value at planned relative time point i

t_i = actual time for planned relative time point i

i = planned relative time of assessment relative to challenge (i.e. 4 hrs, 4.5 hrs, 5 hrs, 5.5 hrs, 6 hrs, 6.5 hrs, 7 hrs, 7.5 hrs, 8 hrs, 8.5 hrs, 9 hrs, 9.5 hrs and 10 hrs)

f = first I

l = last I

- If an observation is missing between two non-missing observations, the AUC will be linearly interpolated between the two non-missing values i.e., the subject's profile will be assumed to be linear between the two available values. No imputation will be made if either the first or last observation is missing.
- If the number of missing values is considered to be substantial, or if the data is not considered to be missing at random, a sensitivity analysis will be carried out with respect to methods of handling missing data in the calculation of the weighted mean.
- The weighted mean will be set to missing for the relevant challenge if any of the following occurs:
 - A short-acting inhaled β -agonist is taken within 8 hours at any time prior to the challenge
 - The dose of allergen administered is different to that of the Screening dose. Note that the dose of allergen used during the treatment period may be modified from the total dose received at screening, for safety reasons, at the discretion of the investigator. However, in this case, the modified dose used must be consistent for all follow up visits. [In these cases the baseline will be set to missing.]
 - The weighted mean LAR will be set to missing if the subject took rescue medication prior to the LAR period i.e., between 0 and 4 hours post-saline.
 - If rescue medication is administered during the LAR period prior to the completion of the 10 hour FEV_1 assessment, all FEV_1 values recorded after the administration of rescue medication for that challenge will be set to the last recorded FEV_1 value prior to the administration of rescue medication. The LAR does not have the same natural recovery as the EAR, hence this is the most appropriate derivation for the LAR. The weighted mean LAR will then be calculated as above, using the imputed data set.
 - If the use of rescue medication is widespread and/or appears to follow a trend, appropriate sensitivity analyses to examine the impact of the derivations may be conducted. For example, if a large number of subjects are rescued at around 8 hours, the weighted mean LAR over 4-8 hours may be derived and analysed as a sensitivity analysis. All sensitivity analyses will be documented in the CPSR.
 - There may be other conditions that effect the LAR response. In such situations it may be necessary to set the respective response to missing. Such scenarios will be

LAR and EAR
identified and documented before unblinding or DBF. Appropriate, sensitivity analyses may be conducted if other situations are noted following unblinding or DBF.
Minimum LAR

 Minimum FEV₁ over 4-10 hrs post-saline challenge will be the minimum value of all the post-saline time points between 4 to 10 hours post-allergen challenge, inclusive of 4 hrs and 10 hrs time points i.e., minimum over 4 hrs, 4.5 hrs, 5 hrs, 5.5 hrs, 6 hrs, 6.5 hrs, 7 hrs, 7.5 hrs, 8 hrs, 8.5 hrs, 9 hrs, 9.5 hrs and 10 hrs. Note that the maximum FEV₁ value at each planned relative time point will be derived, where replicates are taken, for every subject and period, before the minimum values are calculated over the specified time period above. The minimum will be set to missing for the relevant challenge if either of the following occurs: 
 The subject did not receive the correct dose of study medication at any of the 8-weekly visits. A short-acting inhaled β-agonist is taken within 8 hours at any time prior to the challenge. If subject took rescue medication prior to the LAR period i.e. between 0 and 4 hours post-saline administration. The incorrect dose of allergen is administered for the respective BAC. Note that the dose of allergen used during the treatment period may be modified from the total dose received at screening for safety reasons at the discretion of the investigator. However, in this case, the modified dose used must be consistent for all follow up visits. In these cases only the baseline value will be set to missing (essentially removing the subject from any statistical modelling that has the baseline term as a covariate).
There may be other conditions that affect the LAR response. In such situations it may be necessary to set the respective response to missing. Such scenarios will be identified and documented before unblinding. Appropriate, sensitivity analyses may be conducted if other situations are noted following unblinding.
EAR
Weighted Mean EAR

 Weighted mean EAR will be calculated for FEV₁ using the linear trapezoidal rule as per LAR (see above) except using the appropriate EAR time points (i.e., 0 m, 5 m, 10 m, 15 m, 20 m, 30 m, 45 m, 1 hr, 1.5 hrs and 2 hrs). In the event that rescue medication is administered prior to the completion of the 2 hour FEV₁ assessment, the weighted mean will be calculated using only FEV₁ values up to the point of administration of rescue medication. This is considered the most appropriate derivation, given the natural self-limiting profile of the EAR.
Minimum EAR

 Minimum EAR will be calculated for FEV₁ as per LAR (see above) except using the appropriate EAR time points (see above) ie, 0-2 hrs post-saline challenge will be the minimum value of all the post-allergen challenge time points up to and including 2 hours post-allergen challenge i.e., minimum over 5 m, 10 m, 15 m, 20 m, 30 m, 45 m and 1 hr, 1.5 hrs and 2 hrs. Note, saline time point (i.e. 0 hr value) will not be included in this calculation.

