For each treatment arm the (joint) posterior predictive distribution of an individual subject's primary endpoints will be obtained (separate Variance Covariance (VCV) matrices for each treatment arm are preferred to cover the case where variability is also a function of treatment; but there may not be sufficient information in the interim dataset to estimate the required parameters, in which case a pooled VCV matrix across treatment arms would be acceptable). The predictive distributions will be used to simulate a sufficient number of future subjects to achieve the end of study sample size (planned to be 20 per arm, but may be revised upwards to a value between 21 and 30 per arm depending on the observed placebo non-LAR responder rates). Summary statistics (sample mean and sample variance covariance matrix) will be derived using each set of simulated subjects for each treatment. These summary statistics are used as informative prior distributions for the treatment parameters in models fitted to the observed interim data (with the simplifying assumption that these models exclude allergen exposure covariate(s)). If the resulting posterior probability of any attenuation exceeds 0.7 (for either endpoint) the hypothetical end of study result is a success. By repeating the process of simulating sets of future subjects (10,000 times); producing informative priors for the treatment parameters from those simulated subjects and combining with the (unchanging) observed interim dataset in a model to evaluate individual study success an expected probability of a successful outcome can be obtained if the study were allowed to continue past the interim (i.e. the number of simulated sets flagged as successful / total number of simulated sets of subjects).

The advantage of utilising posterior predictive distributions is that they also account for the uncertainty in the true values of the parameters (caused by having to estimate them using only the interim data). Note: Each simulated subject can be thought of as being generated using the average of each of the covariate values. Therefore sample statistics are used as priors for the treatment related parameters only in the subsequent modelling step. This avoids having to generate covariate values for the simulated subjects (e.g. assign them to a centre, or generate a baseline response for them).

Further details are given below:

Interim Analyses to estimate end of study success

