- Active: Sample Mean Vector $\begin{bmatrix} \bar{x}_1 & \bar{x}_2 \end{bmatrix}_{Act}$ Sample VCV $\begin{bmatrix} S_{WM}^2 & S_{WM}S_{Min} \\ S_{WM}S_{Min} & S_{Min}^2 \end{bmatrix}_{Act}$

Interim Analyses to estimate end of study success
--

- In the statistical model fitted to the WM endpoint the priors are:

$$\hat{\mu}_{P,WM} \sim N\left(\bar{x}_{1,Pbo}^{WM}, \frac{S_{WM,Pbo}^2}{Nrem_{Pbo}}\right), \quad \hat{\mu}_{A,WM} \sim N\left(\bar{x}_{1,Act}^{WM}, \frac{S_{WM,Act}^2}{Nrem_{Act}}\right)$$

- In the statistical model fitted to the Min endpoint the priors are

$$\hat{\mu}_{P,Min} \sim N\left(\bar{x}_{2,Pbo}^{Min}, \frac{S_{Min,Pbo}^2}{Nrem_{Pbo}}\right), \quad \hat{\mu}_{A,Min} \sim N\left(\bar{x}_{2,Act}^{Min}, \frac{S_{Min,Act}^2}{Nrem_{Act}}\right)$$

Step 3: Fit model and flag success or failure
--

- To facilitate easy use of the prior distributions a re-parameterized version of Primary analysis Model M3 can be used (Intercept term removed and the zero constraint on the 2nd treatment level removed).
- Separate models will be fitted to each of the endpoints (WM and Min)
- If the posterior probability that $\hat{\mu}_P < \hat{\mu}_A$ exceeds 0.7 (using the informative prior from the ith MCMC iteration) then the ith MCMC iteration is flagged as resulting in a successful end of study result.
- The overall probability of success is the number of successful MCMC iterations / total number of MCMC iterations

Technical details for deriving the individual tables contributing to [Table 2](#)

To determine the probability of success in the presence of non-LAR responders simulations were performed for each possible combination of number of available placebo subjects (n) and number showing no LAR response (r) using the AZ point estimates as the true percentage attenuation (separate procedure for each of the primary endpoints):

Let K represent the number of subjects per arm to be evaluated with each value of K producing a different table and K ranging from 21 to 30 by 1.

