7.1.2 Planned Efficacy Statistical Analyses

Primary Statistical Analyses
Endpoint(s)

 • LAR: minimum <change from saline baseline> FEV₁ between 4-10 hours following allergen challenge 1 week after treatment i.e. FUV1. • LAR: weighted mean of <change from saline baseline> FEV₁ between 4-10 hours following allergen challenge 1 week after treatment i.e. FUV1. 
Note: Text in <> added for clarity, since the wording in the protocol and objectives is familiar to clinical experts in the field, but may be confusing given there are also absolute FEV1 values measured at those times too.
 
 • The “raw” data (replicate (absolute) FEV1 values transcribed into the eCRF) require processing before the Primary analysis. Each planned timepoint may be associated with replicate FEV1 values, which need to be condensed down into a single value (giving a single FEV1 value per timepoint per subject; the timepoints determine how the data are condensed, i.e. some timepoints use the minimum of the replicates others use the maximum). In addition the Screening Visit 2 Incremental BAC challenge may also contain additional FEV1 values relating to the selection procedure for the bolus BAC concentration. Such FEV1 values are not used in the statistical analyses (subjects may differ in the amounts of additional FEV1 data to be excluded). Once the single time profile of absolute FEV1 values is available per subject the Saline baseline is subtracted from each to leave a time profile of change from saline baseline FEV1 values. The minimum and weighted means endpoints are derived from this change from saline baseline time profile. Further details are given in Section 11.5.4. • Any transformation of a response variable is also expected to be applied to the corresponding baseline variable. Final decisions on transformations will be based on the observed data and model diagnostics • Any observations with missing model covariates (e.g. baseline) would be excluded from the model fitting process (i.e. also excluding the record from any centering of covariates)
Model Specification

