- Step 2 (optional): Explore adding other covariate terms to the Step 1 model (for example, but not limited to, Age, Gender, Dose per kg, Blood eosinophil levels). Use expert judgment and changes in DIC to determine final model to take to Step 3. Include any Step 2 models in the listing output and add the associated DIC / changes in DIC values to those produced in Step 1.
- Step 3: For the finally selected model use appropriate combinations of the model parameters (back transforming the combination if necessary) to obtain posterior distributions for the quantities of interest described in the Model Results Presentation. Binary flag variables can be used to evaluate the probability statements, by tracking the instances of the desired event happening over each MCMC iteration and taking the mean of the flag variable as the probability.

For example, if Model 3 is selected then the posterior distribution for the Placebo can be

Primary Statistical Analyses

obtained from adding model parameters Intercept + Treatment[#1] Note: The baseline term is centered and drops out of the expression since it is evaluated at its centered mean of zero; similarly the random centre effect also has mean zero.

The treatment difference (Active – Placebo) would be –Treatment[#1] because the Treatment[#2] parameter is constrained to be zero and the other model terms cancel out.

The Percentage attenuation would be $100 * (1 - (\text{Intercept} / (\text{Intercept} + \text{Treatment}[\#1])))$

The SAS syntax for setting up indicator flags to obtain the probability of any percentage attenuation is Myflag = (pctann > 0); where pctann is the variable storing the Percentage attenuation.

Programming technical note(s): i) Use of flag variables may result in several error/warning messages in the SAS log (for example, but not limited to, warnings about large autocorrelation and/or zero variance); which should be reviewed but may be safely discounted – if in doubt consult the study statistician. ii) To facilitate summary outputs where results from multiple models are displayed simultaneously (large) intermediate datasets from Proc MCMC may need to be stored to ensure consistency (i.e. no differences due to simulation error between model re-runs). Suitable naming conventions should be used to label these files which group related items together.

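### The printed Weighted Mean formula in SAP 11.5.4 has its divisor in the wrong order and mislabels its input; coded as printed, Weighted Mean LAR and EAR would change sign

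*SAP*

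**What the plan says.** SAP 11.5.4 first defines the endpoint in words: "Weighted Mean is defined using the area under the curve divided by the duration of the interval". The detail that follows has the area "divided by the $t_f - t_l$ hrs time interval for each subject", where "t_f = time of first observation, t_l = time for last observation". The displayed formula is half the sum of `(C_{i+1} + C_i)(t_{i+1} - t_i)`, with `t_f - t_l` as denominator. C_i is labelled as the highest FEV1 at planned time i. The same section computes WM EAR by the LAR method on the 0 to 2 h time points.

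On the response scale, SAP 7.1.2 says: "The minimum and weighted means endpoints are derived from this change from saline baseline time profile".

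Success is worded in three places:
- The text of SAP 3.1, on the interim projection: "If the resulting posterior probability of any attenuation exceeds 0.7 (for either endpoint) the hypothetical end of study result is a success".
- Step 3 of the technical table in SAP 3.1: "If the posterior probability that $\hat{\mu}_P < \hat{\mu}_A$ exceeds 0.7", "then the ith MCMC iteration is flagged as resulting in a successful end of study result".
- SAP 7.1.2, on the final analysis: a flag for percentage attenuation above zero, where attenuation is one minus the ratio of the active mean to the placebo mean.

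**The concern.** The time steps in the numerator are positive and the divisor is negative, so the formula returns minus the weighted mean. This contradicts the verbal definition just above it, because a duration is positive. It also contradicts every WM figure in the documents. The Table 2 placebo responses in the protocol run from -0.3749 to -0.9817, the constant for non-LAR responders is -0.20 (SAP 3.1), and the informative prior for the active arm is centred on -0.7081 (SAP 7.1.2).

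At stake is any output that depends on the sign of WM. The Step 3 inequality `mu_P < mu_A` indicates benefit only when a stronger asthmatic response is a more negative number. The C_i label is a second conflict in the same formula, since it names absolute FEV1 where SAP 7.1.2 requires change from saline.

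**Working it through.** **1. The plan's own figures.** Protocol 9.2.1 gives about 78% (Minimum) and 81% (WM) probability of success with 20 completers per arm. Inputs are the eight Table 2 studies (simple means, residual variability read as a variance), attenuations of 18% and 27%, and the 0.7 threshold (z = 0.5244).
- Minimum: difference 0.18 × 1.0504 = 0.1891; SE = √(0.2329 × 2/20) = 0.1526; Φ(0.1891/0.1526 - 0.5244) = 76.3%.
- WM: difference 0.27 × 0.6558 = 0.1771; SE = √(0.1642 × 2/20) = 0.1281; Φ(1.382 - 0.5244) = 80.4%.

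Both are within 2 points of the plan, so the inputs are read correctly, with WM negative.

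**2. The formula.** I use the external-study means implied by the informative priors in SAP 7.1.2: active -0.7081 and placebo -0.7081 - 0.2619 = -0.9700. For a constant profile at half-hour steps from 4 to 10 h, the numerator is 6 × C.

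| Profile (L) | Divisor t_f - t_l = -6 | Divisor t_l - t_f = +6 |
|---|---|---|
| -0.9700 | +0.9700 | -0.9700 |
| -0.7081 | +0.7081 | -0.7081 |

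**3. What a common sign change leaves alone.** The Screening Visit 2 baseline is derived by the same formula, so response and covariate flip together. With fixed-effect priors centred on zero, the fitted model is a mirror image.
- Percentage attenuation: 100 × (1 - 0.7081/0.9700) = 27.0% with either sign.
- Posterior probability of attenuation above zero, for a posterior centred on these means (SD 0.4472, 20 per arm): 0.968 with either sign.
- Minimum LAR does not use this formula. The interim lookup tables use counts of placebo non-LAR responders, not observed WM values.

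**4. What it changes.**
- Active minus placebo: +0.2619 becomes -0.2619, and both arm means change sign.
- Informative-prior analysis (planned for WM only): the prior SD for the active mean is 0.4472/√26 = 0.0877. Data that matched the external study exactly would lie 2 × 0.7081 = 1.4162 L from the prior mean, about 16 prior SDs.
- Step 3: the probability that `mu_P < mu_A`, for the posterior in item 3, goes from 0.968 to 0.032.

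Chance of meeting the Step 3 inequality for WM, 20 per arm, 27% true attenuation:

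| Inputs | Correct sign | As printed |
|---|---|---|
| Table 2 | Φ(1.382 - 0.524) = 80.4% | Φ(-1.382 - 0.524) = 2.8% |
| External-study means, SD 0.4472 | Φ(1.852 - 0.524) = 90.8% | Φ(-1.852 - 0.524) = 0.9% |

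On the second row, a harmful effect of equal size would pass about 91% of the time as printed.

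**5. The C_i label.** With a divisor of t_l - t_f the trapezoidal weights sum to 1. Averaging FEV1 and then subtracting the constant saline value therefore gives the same answer as averaging the change. The label does damage only if the subtraction is left out.

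**6. The summation limit.** A sum over every i from f to l has a last term that needs C at l+1, which does not exist. The limit should be l-1.

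**The case against.** The section uses the f-to-l dash elsewhere as a range label: in the AUC subscript, in the name of the weighted mean and under the summation sign. The sentence on the divisor can be read the same way, as the 4 to 10 h interval. The verbal definition, the sign of every planning figure and the change-from-saline step in SAP 7.1.2 all fix the intent. Literal coding would also show quickly. The planned interim displays include a scatterplot of Minimum against WM with a line of equality (Figure 2.3), by-subject change profiles (Figure 2.29) and a listing of both endpoints (Listing 41). Positive WM values beside negative minima would stand out.

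Most of this stands, and it makes a wrong result unlikely. It does not rescue the displayed fraction, where the dash can only be subtraction. That fraction is the only algebra a programmer has for this endpoint.

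A reader might infer three stronger things that the documents do not support:
- *That the interim success rule is reversed.* Only the Step 3 inequality depends on sign. The text of SAP 3.1 speaks of attenuation, which is unaffected if computed as the SAP's ratio. The projection is optional, and it sits under guidance that the SAP calls non-binding. Success on either endpoint suffices, so Minimum LAR could still carry a beneficial drug.
- *That the final success criterion is wrong.* It is a ratio and does not change under a common sign flip.
- *That an effective drug would show negative attenuation because C_i is raw FEV1.* That requires skipping the saline subtraction that SAP 7.1.2 specifies.

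**Conclusion.** The point holds as a specification error in an operative formula. The printed denominator is first minus last, about -6 h, and the C_i label conflicts with SAP 7.1.2. The harm is conditional on coding the formula as printed. WM LAR and WM EAR would then change sign, and the wrong results would be the WM arm means and differences, the WM informative-prior sensitivity analysis, and the WM comparison in Step 3 of the optional projection.

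The fall from 80.4% to 2.8% (or 90.8% to 0.9%) measures the Step 3 inequality at 20 per arm. It assumes a true 27% attenuation, normal data with a common SD, and Table 2 variability read as a variance. It does not forecast an interim projection, which would mix observed and simulated subjects.

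**What to change.** In SAP 11.5.4:
- Print the divisor as `t_l - t_f` in both the sentence and the formula.
- Sum i from f to l-1.
- Define C_i as the highest replicate FEV1 at time i minus the highest saline FEV1, which is the change from saline already given in SAP 11.4.2.2.
- State that the same definition applies to WM EAR. Weekly TNSS (SAP 11.5.6) borrows the method, so give it the same divisor.

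In SAP 3.1, reword Step 3 as percentage attenuation above zero, so that it matches the text of that section and does not depend on the sign convention.

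The cost is a few lines of SAP text, with no effect on design, sample size or data collection. If the derivation has already been programmed, check that WM values are negative for subjects with an LAR.
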